#### Regorafenib-relevant pathways and targets in ACC

Beyond c-myb mediated activation, several lines of evidence suggest that VEGFR, c-kit, and FGFR pathways are potentially critical to ACC biology.

VEGF pathway: High levels of VEGF ligand have been detected in salivary malignancies in general, and ACC specifically, correlating to more advanced clinicopathologic features (including stage, recurrence, and metastases) in several studies. Multivariate analyses have also shown that high VEGF expression in ACC tumors is an independent prognostic factor for survival. These data suggest that the VEGF pathway may be critical for ACC pathogenesis and/or progression for tumors that overexpress VEGF ligand.

c-kit: c-kit is highly expressed in >90% of ACCs. A 2004 case report described impressive clinical responses in two patients with c-kit positive ACC treated with 600 mg daily of imatinib mesylate, a small molecule inhibitor of c-kit and platelet derived growth factor receptor (PDGFR). While subsequent imatinib studies failed to show significant clinical activity , one requiring "strong" c-kit expression and progressive disease at study entry reported two responses out of 15 evaluable patients. A recent phase II study of dasatinib also failed to produce RECIST responses in ACC patients, though 52% of the patients with progressive disease at study entry did have stable disease on drug. These data indicate that c-kit targeting only has modest efficacy at best, and leaves open the possibility that combining c-kit inhibition with other ACC-relevant kinase targets may produce greater efficacy.

FGF pathway: There is now emerging evidence that the FGF pathway is activated in adenoid cystic carcinomas. Immunohistochemistry revealed that FGF1, FGF2, and FGFR1 are expressed in ACCs, while normal salivary tissues are completely negative or only weakly positive for these proteins. The recent characterization of the genetic landscape of ACCs revealed mutations in FGF16 ligand, FGFR2, and FGFR4 as well as a tandem duplication within FGFR2 discovered in one tumor. Interestingly, transgenic mice overexpressing *FGF8b* develop salivary cancers, and injection of FGF ligand in a 9,10-dimethyl-1,2-benzanthracene (DMBA) carcinogenesis mouse model for salivary malignancies increased the incidence of salivary cancer formation. Such data suggests that the FGF pathway is activated in ACC and may contribute to salivary cancer oncogenesis.

#### Preliminary clinical efficacy data for multi-kinase inhibitors in ACC

Evidence for both MYB-dependent and -independent mechanisms of VEGFR/c-kit/FGFR activation in ACC biology has raised interest in evaluating multikinase inhibitors against

IRB#: 13-244 A(9)

these targets in ACC patients. Preliminarily, studies have suggested clinical activity with these agents. The first study conducted was a phase II trial of sunitinib (VEGFR, PDGFR, KIT inhibitor) in patients with progressive, recurrent/metastatic ACC. While no responses were observed, 8 out of the enrolled 14 patients had stable disease for 6 months or more, potentially meaningful given that progressive disease was required for enrollment. Results from a sorafenib (VEGFR, PDGFR inhibitor) and a dovitinib (VEGFR, PDGFR, FGFR1-3, KIT inhibitor) phase II ACC trial were reported in abstract form at the 2013 ASCO Annual meeting. Both agents elicited an approximately 11% response rate. An axitinib (VEGFR, PDGFR, c-kit inhibitor) phase II study also recently completed enrollment at MSKCC. The data has not yet been presented, but the study was a 2-stage design that met the clinical efficacy rule required for progressing to the second stage. These preliminary data suggest that combined VEGFR, PDGFR, c-kit inhibition plus or minus FGFR targeting translates to some clinical efficacy in ACC.

#### Regorafenib

Regorafenib has potent preclinical antitumor activity and long-lasting anti-angiogenic activity as measured by dynamic contrast enhanced (DCE) – magnetic resonance imaging (MRI).

Regorafenib is a small molecule inhibitor of multiple membrane-bound and intracellular kinases involved in normal cellular functions and in pathologic processes such as oncogenesis, tumor angiogenesis, and maintenance of the tumor microenvironment. In *in vitro* biochemical or cellular assays, regorafenib or its major human active metabolites M-2 and M-5 inhibited the activity of RET, VEGFR1, VEGFR2, VEGFR3, KIT, PDGFR-alpha, PDGFR-beta, FGFR, TIE2, DDR2, Trk2A, Eph2A, RAF-1, BRAF, BRAFV600E, SAPK2, PTK5, and Ab1 at concentrations of regorafenib that have been achieved clinically. In *in vivo* models, regorafenib demonstrated anti-angiogenic activity in a rat tumor model, and inhibition of tumor growth as well as anti-metastatic activity in several mouse xenograft models.

#### Preclinical data with regorafenib

*In vivo*, regorafenib exhibited anti-angiogenic and anti-proliferative effects in human colon and breast xenografts as demonstrated by a reduction in microvessel area, reduced Ki-67 staining, and reduced pERK1/2 staining in tissue sections from tumor xenografts, and dose-dependent inhibition of growth in multiple xenograft models (breast, colon, renal, NSCLC, melanoma, pancreatic, thyroid, ovarian). Immunohistochemical ex-vivo studies with a phospho–specific monoclonal anti-ERK 1 / 2 antibody demonstrated inhibition of the MAPK pathway five days after treatment with regorafenib in 2 of 3 tumor models examined (MDA-MB 231 and BxPC-3), but not in NSCLC (H460).

In addition, all tested human tumor xenografts (MDA-MB-231, H460, BxPC-3 and Colo-205) demonstrated a significant reduction in new blood vessels by histomorphometry as detected in tumor samples using a murine CD31 antibody. These data suggest that regorafenib can target the tumor cell MAPK pathway (tumor cell survival) and tumor vasculature in some but not all tumors.

IRB#: 13-244 A(9)

#### Clinical experience with regorafenib

Two phase III global randomized studies have evaluated the efficacy of regorafenib. The CORRECT (Patients with metastatic colorectal cancer treated with regorafenib or placebo after failure of standard therapy) trial is an international, multicenter, randomized, double-blind, placebo-controlled study that enrolled 760 patients with mCRC whose disease has progressed after approved standard therapies. Metastatic colorectal cancer patients were randomized to regorafenib plus best supportive care (BSC) or placebo plus BSC. Treatment cycles consisted of 160 mg of regorafenib (or matching placebo) once daily for three weeks on / one week off plus BSC. The primary endpoint of this trial was overall survival. Secondary endpoints included progression-free survival, objective tumor response rate and disease control rate. The safety and tolerability of the two treatment groups were also compared.

At a preplanned second interim analysis, there was a statistically significant survival benefit for regorafenib. The estimated hazard ratio for overall survival was 0.773 (95% confidence interval [CI], 0.635 to 0.941; 1-sided p = .0051). Patients treated with regorafenib had a median overall survival of 6.4 months, compared with 5.0 months for placebo — a 29% increase in survival. In addition to improved overall survival, progression-free survival was superior; median progression-free survival was 1.9 months (95% CI, 1.88 to 2.17) for regorafenib and 1.7 months (95% CI, 1.68 to 1.74) for placebo. The estimated hazard ratio for progression-free survival was 0.493 (95% CI, 0.418 to 0.581; 1-sided p< .000001). There was a substantial difference in disease control rate in the regorafenib and placebo groups (44% vs. 15%; p<.000001). Regorafenib demonstrated comparable efficacy benefits across patient subgroups analyzed including age, number of mets, number of lines of prior therapy, and kras status.

The most frequent grade 3+ adverse events in the regorafenib group were hand–foot skin reaction (17%), fatigue (15%), diarrhea (8%), hyperbilirubinemia (8%), and hypertension (7%). The efficacy and safety from the CORRECT study supported FDA approval in September 2012.

The efficacy and safety of regorafenib were examined in the Phase III GRID trial in patients with gastrointestinal stromal tumors (GISTs) who had exhausted all other treatment options. The study involved 199 patients with metastatic and/or unresectable GIST that had become resistant to imatinib and sunitinib. Patients were randomized 2:1 to regorafenib (160 mg orally once daily on a 3 weeks on/1 week off cycle) or placebo, plus best supportive care.

The results showed that treatment with regorafenib led to a statistically significant 3.9-month improvement in progression-free survival (PFS), compared with placebo (4.8 months vs. 0.9 months; hazard ratio [HR] = 0.27; p < .0001). Overall survival was statistically similar between groups as expected due to a trial design that allowed crossover to regorafenib for disease progression (85% for placebo and 31% regorafenib randomized patients). The median survival period without tumor growth among patients on regorafenib was 4.8 months while for the control group on placebo it was less than a month. The overall disease control rate combining partial responses with durable stable disease for at least 12 weeks was 53% with regorafenib compared with 9% in the control

IRB#: 13-244 A(9)

group. The most common grade ≥3 adverse events associated with regorafenib were hand-foot skin reaction (56.1%), hypertension (48.5%), and diarrhea (40.9%). The efficacy and safety of the GRID study data supported FDA approval February 2013.

#### 4.0 OVERVIEW OF STUDY DESIGN/INTERVENTION

#### 4.1 Design

This is a single-arm phase II study of patients with progressive, recurrent/metastatic adenoid cystic carcinoma (R/M ACC) treated with regorafenib. There are two primary objectives for the study: 1) to determine the proportion of patients alive at 6 months without disease progression by RECIST v1.1 criteria (6-month PFS), and 2) to determine the best overall response rate (BOR = CR+PR) documented by RECIST v1.1 criteria. Thirty-eight patients will be enrolled in the study. If at least 21 patients are alive and free of progression at 6-month, or if at least 5 patients have a response at any time while being enrolled in the study, the regimen will be considered worthy of further investigation. Regorafenib safety and tolerability will be assessed utilizing Common Terminology Criteria for Adverse Events version 4.0 (CTCAE 4.0) as a secondary endpoint. An exploratory objective is to analyze tumor tissue in order to identify potential biomarkers that correlate to regorafenib clinical efficacy.

#### 4.2 Intervention

All eligible patients will receive a starting regorafenib dose of 120 mg daily taken orally for 3 weeks in a 4-week cycle. Patients for whom regorafenib dose reduction was not performed or required may have their treatment dose increased to the FDA-approved dose of 160 mg daily orally for 3 weeks in a 4-week cycle in cycle #2 or beyond (this is not mandatory). RECIST v1.1 tumor assessments will be made at baseline (CT or MRI) and then approximately every 2 cycles (or every 8 weeks (+/- 1 week)). After 10 months, imaging will be done every 3 cycles (or every 12 weeks (+/- 1 week)). Patients may remain on study until progression of disease or unacceptable toxicity

#### 5.0 THERAPEUTIC/DIAGNOSTIC AGENTS

Regorafenib (Bayer) or its major human active metabolites M-2 and M-5 inhibits the activity of RET, VEGFR1, VEGFR2, VEGFR3, KIT, PDGFR-alpha, PDGFR-beta, FGFR1, FGFR2, TIE2, DDR2, Trk2A, Eph2A, RAF-1, BRAF, BRAFV600E, SAPK2, PTK5, and Ab1 at concentrations of regorafenib that have been achieved clinically.

Regorafenib tablets will be packaged in high density polyethylene bottles with a white child resistant closure and induction seal. Each bottle includes 30 tablets and a 3-gram desiccant. The bottles will have a label affixed containing study identification, product identification, and quantity of tablets. Once the drug has been received it must be kept in a secure, dry location. Study drug must be stored in its original bottle at a temperature not above 25°C (77°F). The study drug must be exclusively used for the investigation specified in this protocol and it will only be accessible to authorized staff.

#### 6.0 CRITERIA FOR SUBJECT ELIGIBILITY

IRB PB

IRB#: 13-244 A(9)

#### 6.1 Subject Inclusion Criteria

- Patients must have pathologically or cytologically confirmed adenoid cystic carcinoma.
   Cancers arising from non-salivary gland primary sites are allowed.
- Patients must have recurrent and/or metastatic disease not amenable to potentially curative surgery or radiotherapy.
- At least 2 weeks must have elapsed since the end of prior systemic treatment (4 weeks for bevacizumab- containing regimens) or radiotherapy with resolution of all treatment-related toxicity to NCI CTCAE Version 4.0 grade ≤1 (or tolerable grade 2) or back to baseline (except for alopecia, lymphopenia, or hypothyroidism). Any number of prior therapies for recurrent/metastatic ACC are allowed.
- Patients must have RECIST v1.1 measurable disease, defined as at least one lesion that
  can be accurately measured in at least one dimension (longest diameter to be recorded
  for non-nodal lesions and short axis for nodal lesions) as ≥20 mm with conventional
  techniques or as ≥10 mm with spiral CT scan.
- Patients must have documentation of a new or progressive lesion on a radiologic imaging study performed within 6 months prior to study enrollment (progression of disease over any interval is allowed) and/or new/worsening disease related symptoms within 6 months prior to study enrollment. Note: This assessment will be performed by the treating investigator. Evidence of progression by RECIST criteria is not required.
- Patients must have archival tissue from the primary tumor or metastases available for correlative studies. Either a paraffin block or twenty unstained slides are acceptable. If twenty slides are not available, a lesser amount may be acceptable after discussion with the Principal Investigator, [name].
- Patients must agree to undergo biopsy of a malignant lesion. Biopsies do not need to be
  done if either the investigator or person performing the biopsy judges that no tumor is
  accessible for biopsy or that biopsy poses too great of a risk to the patient. Patients may
  also be exempt if frozen tumor tissue has been collected within 12 months of study
  enrollment that the Principal Investigator deems is appropriate/sufficient for analysis on
  this protocol.
- Age ≥ 18 years.
- ECOG performance status ≤2 (Karnofsky ≥60%, see Appendix A).
- Life expectancy of at least 12 weeks (3 months) as determined by the investigator.
- Subjects must be able to understand and be willing to sign the written informed consent form. A signed informed consent form must be appropriately obtained prior to the conduct of any trial-specific procedure.
- Adequate bone marrow, liver and renal function as assessed by the following laboratory requirements:

IRB PB

IRB#: 13-244 A(9)

- Total bilirubin ≤ 1.5 x the upper limits of normal (ULN)
- Alanine aminotransferase (ALT) and aspartate amino-transferase (AST)  $\leq$  2.5 x ULN ( $\leq$  5 x ULN for subjects with liver involvement of their cancer)
- Alkaline phosphatase limit ≤ 2.5 x ULN (≤ 5 x ULN for subjects with liver involvement of their cancer)
- Lipase ≤ 1.5 x the ULN
- Amylase ≤ 1.5 x the ULN
- o Serum creatinine ≤ 1.5 x the ULN or calculated creatinine clearance >60 ml/min
- Platelet count ≥ 100,000 /mm3, hemoglobin (Hb) ≥ 9 g/dL, absolute neutrophil count (ANC) ≥1500/mm3. Blood transfusion to meet the inclusion criteria will not be allowed.
- Women of childbearing potential must have a negative serum pregnancy test performed within 2 weeks prior to the start of study drug. Post-menopausal women (defined as no menses for at least 1 year) and surgically sterilized women are not required to undergo a pregnancy test.
- Subjects (men and women) of childbearing potential must agree to use adequate contraception beginning at the signing of the consent form until at least 3 months after the last dose of study drug. The definition of adequate contraception will be based on the judgment of the principal investigator or a designated associate.
- Subject must be able to swallow and retain oral medication.

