#### 12.1 Definitions

Evaluable for toxicity. All patients will be evaluable for toxicity from the time of their first treatment with regorafenib.

Evaluable for objective response. Only those patients who have measurable disease present at baseline and have received at least one dose of therapy will be considered evaluable for response. These patients will have their response classified according to the definitions stated below. (Note: Patients who exhibit objective disease progression prior to the end of cycle 1 will also be considered evaluable.)

Evaluable Non-Target Disease Response. Patients who have lesions present at baseline that are evaluable but do not meet the definitions of measurable disease, have received at least one cycle of therapy, and have had their disease reevaluated will be considered evaluable for non-target disease. The response assessment is based on the presence, absence, or unequivocal progression of the lesions.

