#### 12.2 Disease Parameters

Measurable disease. Measurable lesions are defined as those that can be accurately measured in at least one dimension (longest diameter to be recorded) as  $\geq$ 20 mm by chest x-ray, as  $\geq$ 10 mm with CT scan, or  $\geq$ 10 mm with calipers by clinical exam. All tumor measurements must be recorded in millimeters (or decimal fractions of centimeters).

Note: Tumor lesions that are situated in a previously irradiated area are not considered measurable unless there has been demonstrated progression in the lesion.

Malignant lymph nodes. To be considered pathologically enlarged and measurable, a lymph node must be >15 mm in short axis when assessed by CT

(RB PB

IRB#: 13-244 A(9)

scan (CT scan slice thickness recommended to be no greater than 5 mm). At baseline and in follow-up, only the short axis will be measured and followed.

Non-measurable disease. All other lesions (or sites of disease), including small lesions (longest diameter <10 mm or pathological lymph nodes with ≥10 to <15 mm short axis), are considered non-measurable disease. Bone lesions, leptomeningeal disease, ascites, pleural/pericardial effusions, lymphangitis cutis/pulmonitis, inflammatory breast disease, and abdominal masses (not followed by CT or MRI), are considered as non-measurable.

Note: Cystic lesions that meet the criteria for radiographically defined simple cysts should not be considered as malignant lesions (neither measurable nor non-measurable) since they are, by definition, simple cysts.

'Cystic lesions' thought to represent cystic metastases can be considered as measurable lesions, if they meet the definition of measurability described above. However, if non-cystic lesions are present in the same patient, these are preferred for selection as target lesions.

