Target lesions. All measurable lesions up to a maximum of 2 lesions per organ and 5 lesions in total, representative of all involved organs, should be identified as **target lesions** and recorded and measured at baseline. Target lesions should be selected on the basis of their size (lesions with the longest diameter), be representative of all involved organs, but in addition should be those that lend themselves to reproducible repeated measurements. It may be the case that, on occasion, the largest lesion does not lend itself to reproducible measurement in which circumstance the next largest lesion which can be measured reproducibly should be selected. A sum of the diameters (longest for non-nodal lesions, short axis for nodal lesions) for all target lesions will be calculated and reported as the baseline sum diameters. If lymph nodes are to be included in the sum, then only the short axis is added into the sum. The baseline sum diameters will be used as reference to further characterize any objective tumor regression in the measurable dimension of the disease.

Non-target lesions. All other lesions (or sites of disease) including any measurable lesions over and above the 5 target lesions should be identified as **non-target lesions** and should also be recorded at baseline. Measurements of these lesions are not required, but the presence, absence, or in rare cases unequivocal progression of each should be noted throughout follow-up.

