#### 12.4.2 Evaluation of Non-Target Lesions

Complete Response (CR): Disappearance of all non-target lesions and

normalization of tumor marker level. All lymph nodes must be non-pathological in size (<10 mm short axis). Note: If tumor markers are initially

above the upper normal limit, they must normalize for a patient to be considered in

complete clinical response.

Non-CR/Non-PD: Persistence of one or more non-target lesion(s)

and/or maintenance of tumor marker level above

the normal limits.

Progressive Disease (PD): Appearance of one or more new lesions and/or

unequivocal progression of existing non-target lesions. Unequivocal progression should not normally trump target lesion status. It must be representative of overall disease status change,

not a single lesion increase.

Although a clear progression of "non-target" lesions only is exceptional, the opinion of the treating physician should prevail in such circumstances, and the progression status should be confirmed at a later time by the review panel (or Principal Investigator).

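### Section 6.1 admits lymph nodes of 10 mm short axis as measurable disease, but Section 12.2 classes nodes of 10 to under 15 mm as non-measurable, so an eligible patient can lack any target lesion for the response co-primary

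*Combined protocol and SAP*

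**What the plan says.** **Entry rule (Section 6.1).** The criterion opens with "Patients must have RECIST v1.1 measurable disease, defined as at least one lesion that" can be accurately measured, and then gives the sizes. Nodes are named inside the same sentence, "for non-nodal lesions and short axis for nodal lesions) as ≥20 mm with conventional", which continues "techniques or as ≥10 mm with spiral CT scan". No separate nodal threshold appears anywhere in Section 6.1.

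**Assessment rule (Section 12.2).** To be measurable, "a lymph node must be >15 mm in short axis when assessed by CT". In the paragraph on non-measurable disease, "pathological lymph nodes with ≥10 to <15 mm short axis), are considered non-measurable disease".

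**What depends on measurability.**
- Target lesions are drawn from measurable lesions only: "All measurable lesions up to a maximum of 2 lesions per organ and 5 lesions in total" (Section 12.2).
- Partial response is a fall of at least 30% in the target-lesion sum (Section 12.4.1).
- The table for patients with non-measurable disease (Section 12.4.3) offers CR, non-CR/non-PD, not evaluated or PD. It has no PR row.
- Response evaluability is limited by Section 12.1: "Only those patients who have measurable disease present at baseline and have received at least one dose of therapy".
- Section 14 includes every patient who takes at least one dose in the evaluation of both primary objectives.

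**Decision rule (Section 14).** BOR null 5%, alternative 20%, one-sided type I error 5%, power 90%, at least 5 responses among 38 patients.

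**The concern.** The entry rule and the endpoint rule classify the same node differently. A patient whose only qualifying lesion is a node of 12 mm short axis on spiral CT meets Section 6.1 as written, and under Section 12.2 has no measurable lesion and so no target lesion.

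BOR is a co-primary endpoint decided by five responders, and the design has almost no slack above its stated power. A patient who cannot have a PR takes a place among the 38 and contributes little or nothing to the chance of reaching five. Sections 12.1 and 14 also disagree about whether this patient counts in the response rate, and the plan does not say which governs.

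**Working it through.** **Step 1. Follow one patient through the text.** Suppose the only qualifying disease is a node of 10 to under 15 mm short axis on spiral CT.

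| Question | Section | Answer |
|---|---|---|
| Eligible on measurable disease? | 6.1 | Yes (at least 10 mm, short axis) |
| Node measurable? | 12.2 | No (not above 15 mm; inside the listed non-measurable range) |
| Any target lesion? | 12.2 | No |
| PR possible? | 12.4.1, 12.4.3 | No |
| Evaluable for response? | 12.1 | No |
| In the primary denominator? | 14 | Yes, once dosed |

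**Step 2. The 15 mm edge.** The measurable limit is above 15 mm and the listed non-measurable range stops below 15 mm. A node of exactly 15 mm meets neither figure. The general opening of the non-measurable paragraph (all other lesions) would sweep it in, but the numbers themselves do not meet.

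**Step 3. Reproduce the plan's figure.** Inputs from Section 14: n = 38, at least 5 responses, null 0.05, alternative 0.20. Exact binomial:
- Type I error = P(X ≥ 5 | 38, 0.05) = 0.0397
- Power = P(X ≥ 5 | 38, 0.20) = 0.901

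Both meet the stated 5% and 90%. A search over n from 20 to 44 finds 38 to be the smallest that does so. The stated design is correct.

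**Step 4. Illustration.** Let k of the 38 be unable to respond. The value of k is an assumption, because the documents give no figure. Keep the rule of at least 5 and let the other 38 − k respond at the design rates:
- Power = P(X ≥ 5 | 38 − k, 0.20)
- Type I error = P(X ≥ 5 | 38 − k, 0.05)

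| k | 38 − k | Power | Type I error |
|---|---|---|---|
| 0 | 38 | 90.1% | 4.0% |
| 1 | 37 | 88.8% | 3.6% |
| 2 | 36 | 87.3% | 3.2% |
| 3 | 35 | 85.7% | 2.9% |

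One such patient costs 90.1 − 88.8 = 1.3 points of power; three cost 90.1 − 85.7 = 4.4 points. Type I error goes down.

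**Step 5. The CR route.** Section 12.4.2 sets the nodal size for a non-target CR: "All lymph nodes must be non-pathological in size (<10 mm short axis"). A node of 10 mm that reads 9 mm meets that size. Suppose one such patient is scored CR in error with probability q (an assumption), and the other 37 respond at the null rate:

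Type I error = q × P(X ≥ 4 | 37, 0.05) + (1 − q) × P(X ≥ 5 | 37, 0.05) = q × 0.1119 + (1 − q) × 0.0359

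This gives 3.97% at q = 5%, 4.35% at q = 10%, 5.11% at q = 20% and 5.87% at q = 30%. It passes 5% only when q is a little under 20%.

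**The case against.** **The label already settles it.** Section 6.1 names RECIST v1.1, Section 12 evaluates response by that guideline, and Section 12.2 sets out the nodal limit, so an investigator may apply the larger limit at entry. That may happen in practice. It does not cure the text: the definition written after the label includes nodes at 10 mm, and Section 15.1 has eligibility confirmed against the eligibility criteria.

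**The group may be empty.** Only patients with no non-nodal lesion of 10 mm or more on CT and no node above the Section 12.2 limit are affected. The documents give no frequency, and zero is compatible with all of them. This stands, and it is why the power figures are an illustration.

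**Such a patient can still reach CR.** This also stands. Treating the patient as unable to respond slightly overstates the power loss.

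**A stronger reading: inflated type I error.** A reader might infer that a 1 mm change in a 10 mm node would produce false complete responses and raise type I error to P(X ≥ 4 | 37, 0.05) = 11.2%. The documents do not support that. The 11.2% is the chance of passing given that a false CR has certainly occurred; weighted by its probability, the figures are those in Step 5 of the working. The route is also restricted. Section 12.1 makes the patient not evaluable for response. Section 12 asks for confirmation at least 4 weeks later, and Section 12.4.3 makes best response depend on it. All other non-target disease must disappear. A 14 mm node must shrink by more than 4 mm. Nor can the power loss and the type I inflation both apply in full to the same patient.

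**The denominator is a separate issue.** In part. Any wider tension between Sections 12.1 and 14 does not depend on node size, but for this patient the two sections give opposite answers.

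**Conclusion.** The plan is wrong as written: Sections 6.1 and 12.2 contradict each other on nodes of 10 to under 15 mm, and the numerical nodal limits in Section 12.2 leave out exactly 15 mm. Followed literally, the text lets a patient in who has no target lesion and no route to PR, and who still counts among the 38.

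Severity is low. The size rests on an unknown k. With k from 1 to 3, and those patients assumed unable to respond at all, BOR power is 88.8% to 85.7% against 90.1%. With k = 0 nothing changes. The sample size and the rule of 5 in 38 are correct. The 6-month PFS co-primary is less affected, because progression can still be called on new lesions or unequivocal non-target progression, although the 20% target-sum criterion would not apply. A claim of materially inflated type I error should not be made.

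**What to change.** 1. In Section 6.1, let nodes count as measurable only at the nodal short-axis limit in Section 12.2, and keep 10 mm for non-nodal lesions on CT. A direct cross-reference to Section 12.2 would keep the two from drifting apart again.
2. In Section 12.2, word the measurable nodal limit so that it meets the under-15 mm non-measurable range with no gap, so that a node of exactly 15 mm is classified by the numbers.

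With the first change, everyone eligible as written has a potential target lesion, and the conflict between Sections 12.1 and 14 no longer arises by this route. Neither the sample size nor the decision rule changes.

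The cost is a wording change in an amendment. The downside is that a few patients whose only qualifying disease is nodes of 10 to under 15 mm would no longer qualify.
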